### 5.3 Unique Study Identification Code Assignment

Each subject will be assigned a unique study identification code in an effort to protect subject confidential information. The unique study ID will be used to link study data and other study information to the subject in lieu of the subject name. The Subject Name Log will be used to link the unique study ID to the subject.

This log will remain confidential and will not be provided to the Sponsor, but only used for reference when monitoring at the study site.

### 5.4 Medication Regimen

It is recommended that subjects be started on dual anti-platelet therapy (DAPT) at least 1 week before the procedure or adequately pre-loaded with DAPT according to the institution's practice. Administration of anticoagulation medication and monitoring of activated clotting time (ACT) per institution guidelines is to be performed throughout the procedure. It is recommended that an Activated Clotting Time of at least 200 seconds is maintained for the duration of the index procedure. It is recommended that dual anti-platelet and/or anti-coagulant therapy be prescribed for a minimum of 3 months post-procedure.

### 5.5 Enrollment (Day 0)

Once any component of the LimFlow System is introduced into the body, the subject will be considered to be enrolled in the study. If any LimFlow device is introduced but stent-graft implantation is either not attempted or unsuccessful, subjects will be followed for safety for 30 days with a minimum of phone calls to assess Primary Endpoint of AFS.

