	Baseline and Screening (-6M to proc)	Treatment (Day 0) to Discharge	2 Weeks (+/- 3 Days)	1 Month (+/- 1 week)	2 Month (+/- 2 weeks)	3 Month (+/- 2 weeks)	6 Month (+/- 2 weeks)	9 Month (+/- 2 weeks)	1 Year (+/- 4 weeks)	2 Year (+/- 4 weeks)	3 Year (+/- 4 weeks)
Written Informed Consent	√										
Baseline imaging  that establishes pedal artery target	√										
Inclusion / Exclusion criteria, including IRC, assessment that subject is not a candidate for conventional surgical or endovascular limb salvage procedures	√										
Demographic data, medical history, medication review, physical exam, and pregnancy test (if applicable)	√										
Additional exams if required to confirm eligibility 	√										
Pedal vein assessment for case planning	√										
Review of medications / dual anti-platelet regimen 	√	√	√	√		√	√	√	√	√	√
Rutherford Classification (RCC)	√			√		√	√	√	√	√	√
WIFI Classification (ischemia measured via TcPO 2  or Toe Pressure)	√		√	√		√	√	√	√	√	√
Wound healing assessment, and photographs 	√		√	√		√	√	√	√	√	√
Wound culture, if suspected infection 	√	√	√	√		√	√	√	√	√	√
Pulse evaluation via hand-held continuous wave Doppler distal to the stent graft 		√ 	√	√		√	√	√	√	√	√
Serum Creatinine	√			√			√				
Numeric Pain Scale Rating (1-10)	√			√		√	√	√	√	√	√
Procedural angiogram  and device performance data		√									
Procedure time, defined from sheath insertion to final catheter removal		√									
Fluoroscopy and Contrast for the index procedure		√									
Device- or procedure-related AE and SAEs 		√	√	√	√	√	√	√	√	√	√
Assessment of amputation and/or re-intervention of the Stent Graft			√	√		√	√	√	√	√	√
Duplex Ultrasound Exam to assess Stent Graft patency 				√	√	√	√	√	√	√	√
All-cause mortality		√	√	√	√	√	√	√	√	√	√

 E.g., an angiogram without procedure or angiogram from a failed recanalization  
 Including an MRI, if there is suspected osteomyelitis and bypass conduit vein mapping if there is a pedal artery target and the ipsilateral saphenous vein has not been previously harvested  
 Dual antiplatelet therapy is recommended for 3 months post-procedure. At a minimum, all subjects are recommended to be started on DAPT at least one week before procedure or adequately pre-loaded with DAPT as per institution practice.  

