 TcPO2 will be measured at 2 constant points on the dorsum of the midfoot through the 12-month follow-up at sites who perform TcPO2.  
 Prior to any re-intervention of the stent graft, an angiogram/image and wound photograph should be obtained for adjudication purposes.  
 Optional; Sponsor will reimburse for culture any time there is a suspected infection.  
 Hand-held continuous wave Doppler will be performed immediately post-procedure and again between 4 and 30 hours post-procedure to assess for acute thrombosis; any findings of acute thrombosis in this time frame must be reported to the Sponsor within 24 hours of the exam.  
 Must include pre- and post-index arteriogram showing vasculature from hip to foot  
 Review of any hospitalizations or procedures involving the index limb, and/or potentially related to the device or procedure; all SAEs through 6 months. For subjects out of area or who refuse to come in for a visit, a telephone assessment should be conducted to capture as much information as possible at the time point.  
 If any LimFlow device is introduced but stent-graft implantation is either not attempted or unsuccessful, subjects will be followed for safety for 30 days with a minimum of phone calls to assess AFS.  
 May be performed at any additional non-study visit as standard of care, as indicated by clinical symptoms.

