### 5.9 Study Exit or Premature Withdrawal

Subjects will be exited from the study by completion of a Study Exit eCRF. Subjects will be exited upon completion of the follow-up visits, withdrawal of consent, or instance of meeting a primary study endpoint (major amputation or death). Following study exit, the subject will undergo the standard medical care for their condition as determined necessary and appropriate by their physician.

Subjects may be prematurely exited or withdrawn from the study for, including but not limited to, the following reasons:

- Voluntary withdrawal – meaning that the subject voluntarily chooses not to further participate in the study
- Lost to follow-up – meaning that the subject is more than 14 days out of window of a study visit and 3 documented attempts to contact the subject are unsuccessful. A subject who misses two consecutive study visits, including phone contact, will be considered lost to follow-up. A missed visit will be considered a protocol deviation and the deviation will be documented and reported.
- In the physician’s opinion, it is not in the best interest of the subject to continue study participation.

All subjects enrolled (including those withdrawn or lost to follow-up) shall be accounted for and documented.

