### 8.5 General Reporting Requirements (Serious & Non-Serious Adverse Events)

All potentially device- and/or procedure-related adverse events (AE) and all serious adverse events (SAE) will be reported and monitored from the time of treatment through the 6-month follow-up visit. Any SAEs related to the index limb will be reported and monitored throughout the 3-year follow-up visit. The report should include: severity, duration, action taken, treatment outcome and relationship of the adverse experience to the study device, procedure, concomitant medications, pre-existing condition, etc. (i.e., unrelated, related or relationship unknown).

In the case of device- and/or procedure-related adverse events that require adjudication by the CEC, medical record source documentation (e.g., procedure notes, operative notes, discharge summary, relevant progress notes, imaging, photos, or lab studies) must be provided to Sponsor or its designee.

It is the responsibility of the investigator to inform their IRB/EC of serious adverse events as required by their IRB/EC procedures and in conformance with FDA and local regulatory requirements.

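### Subjects with a failed or non-attempted implant are in the primary 180-day AFS population, but the protocol gives them only a 30-day follow-up period and no end date for the AFS calls

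*Protocol*

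**What the plan says.** Protocol section 5.5 treats a subject as enrolled once any part of the LimFlow System is introduced. For those whose stent graft is then not implanted, it says "subjects will be followed for safety for 30 days with a minimum of phone calls to assess Primary Endpoint of AFS". Table 1 footnote 10 repeats the rule: "subjects will be followed for safety for 30 days with a minimum of phone calls to assess AFS". Neither sentence says when the calls end.

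Protocol section 11.4 and SAP section 5.1 put every subject with an introduced device in the mITT population whatever the technical result, and SAP 5.1 names mITT as primary. SAP section 6 sets the endpoint as AFS at 180 days.

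Other provisions point to longer follow-up:

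- The protocol synopsis (Duration of Study) has each enrolled subject followed for up to 3 years.
- Protocol 11.5.2 and SAP 6.4 place the final analysis after all enrolled subjects could have reached 180 days.
- Protocol 8.5 says "all serious adverse events (SAE) will be reported and monitored from the time of treatment through the 6-month follow-up visit", and Table 1 footnote 9 says "all SAEs through 6 months".
- Protocol 5.9 says "Subjects will be exited upon completion of the follow-up visits, withdrawal of consent, or instance of meeting a primary study endpoint"; neither this sentence nor the section's list of premature-exit examples names a failed implant.
- In Table 1, footnote 10 hangs on the row "Device- or procedure-related AE and SAEs 9,10". The rows "Assessment of amputation and/or re-intervention of the Stent Graft" and "All-cause mortality" do not carry it and run to the 3-year visit.

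**The concern.** Section 5.5 and footnote 10 are the two sentences written for this subgroup, so a site coordinator will look there first, and both can be read as a stop at day 30. Events up to day 30 are counted either way. The question is what happens to a failed implant who is event-free at day 30.

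If contact stops, that subject falls in Group C of SAP section 6.5. The 180-day status is then drawn from a piecewise exponential model with one pooled hazard and no term for implant status. If all failed implants stop at day 30, the hazard after day 30 is estimated from implanted subjects alone. AFS is overstated if failed implants do worse after day 30, unbiased if prognosis is equal, and understated if they do better. Protocol section 10.1 says the actual benefits are unknown, so the direction cannot be presumed.

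The SAP's operating characteristics do not cover this pattern: section 6.7 simulates 10% loss at random, uniform over the 180 days.

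**Working it through.** **1. The plan's own figures.** The SAP 6.7 hazards give cumulative hazard 30 × 0.005417298 = 0.1625 at day 30, so S(30) = 0.85. Over 180 days the sum is 0.1625 + 0.1942 + 0.1214 + 0.1382 = 0.6162 (before rounding the terms), so S(180) = 0.54. Both match the SAP. The share of 180-day events falling after day 30 is (0.85 − 0.54)/(1 − 0.54) = 67%.

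With a Beta(1,1) prior and threshold 0.977, success at N=105 needs 67 event-free subjects: the posterior probability is 0.9779 with 67 and 0.9652 with 66.

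**2. Assumptions, none of them stated in the documents.** Contact stops at day 30 for every failed implant. The failed share q is 3%, 5% or 10%. AFS in failed implants, f, is 42.3% (the historical rate in protocol 11.2.2), varied below. True mITT AFS is 0.54. Each group has the SAP hazard shape, scaled to its own AFS.

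**3. Formula.**

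bias = q × S_f(30) × [S_imp(180)/S_imp(30) − S_f(180)/S_f(30)], with implanted AFS S_imp(180) = (0.54 − q·f)/(1 − q)

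For f = 0.423 the scale factor is ln 0.423 / ln 0.54 = 1.396. Then S_f(30) = 0.85^1.396 = 0.797, and true AFS given event-free at day 30 is 0.423/0.797 = 0.531.

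For q = 10%, implanted AFS is (0.54 − 0.0423)/0.90 = 0.553 and S_imp(30) = 0.855, so the imputed conditional AFS is 0.647. The bias is 0.10 × 0.797 × (0.6465 − 0.5308) = 0.0092. At N=105, about 105 × 0.10 × 0.797 = 8.4 failed implants are event-free at day 30, and imputation adds about 8.4 × 0.1157 = 0.97 successes.

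**4. Type I error.** Paired simulations used the same simulated subjects with and without the day-30 stop: 40,000 trials per scenario, 10% uniform loss to follow-up, and the SAP priors and threshold. The adaptive version uses the maximum of 105, 5 per month after ramp-up, the SAP stopping thresholds, and the futility probability at N=120.

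| q | f | Bias (points) | Fixed N=105: day-30 stop vs day 180 | Adaptive: day-30 stop vs day 180 |
|---|---|---|---|---|
| 3% | 42.3% | +0.26 | 0.0248 vs 0.0224 | 0.0278 vs 0.0243 |
| 5% | 42.3% | +0.44 | 0.0263 vs 0.0215 | 0.0288 vs 0.0241 |
| 10% | 42.3% | +0.92 | 0.0333 vs 0.0216 | 0.0365 vs 0.0236 |
| 10% | 51.1% | +0.24 | 0.0262 vs 0.0219 | 0.0289 vs 0.0254 |
| 5% | 33.5% | +0.74 | 0.0313 vs 0.0220 | 0.0331 vs 0.0249 |
| 10% | 54% (equal) | 0 | 0.0237 vs 0.0231 | 0.0245 vs 0.0242 |
| 10% | 59.7% | −0.47 | 0.0185 vs 0.0222 | 0.0217 vs 0.0264 |

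The values 33.5% and 51.1% are the limits of the historical 95% interval. The value 59.7% is the pooled rate before risk adjustment, from a mix that includes Rutherford 4.

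**5. Calibration.** Against SAP Table 2, the adaptive simulation gives null type I error 0.0260 (SE 0.0011; SAP 0.0239) and average N 74.9 (74.8). At AFS 0.70 it gives power 0.901 (0.9051) and average N 82.8 (82.5). Because the day-180 rates themselves range from 0.0236 to 0.0264, read the paired differences rather than the absolute values against 0.025. For f = 42.3% the adaptive differences are 0.0035, about 0.005 (SE 0.0005) and 0.0129 (SE 0.0007) at 3%, 5% and 10% failures.

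**The case against.** The best defence is that section 5.5 supplies its own time point. The calls are to assess the primary endpoint, AFS is defined as that endpoint only at 6 months, and a day-30 call cannot assess it. On this reading the 30 days limit safety reporting and AFS is followed at least by phone. The placement of footnote 10 supports this: it sits on the adverse-event row and not on the amputation or mortality rows. Some of the conflicting provisions are also soft. Up to 3 years is a maximum, and the opportunity to reach 180 days governs when the analysis occurs rather than guaranteeing contact with each subject.

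This reading is plausible, and if it is what sites do, the effect on AFS is nil. But no sentence gives the calls an end date. A 30-day safety limit would also still have to be squared with the six-month SAE collection in section 8.5 and footnote 9.

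It is also fair that the numbers rest on inputs the documents do not give, that the range includes zero and negative bias, and that at 3% to 5% failures with f = 42.3% the shift is under half a subject in 105.

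Finally, safeguards exist. The tipping-point analysis (protocol 11.5.3, SAP 9.1.1) includes the combination that counts every unknown failed implant as an event, and the reasons for missing data will be described. These show sensitivity to a missing outcome; they do not recover it. The per-protocol set excludes unsuccessful procedures and does not help.

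**Conclusion.** The concern holds as a matter of text. The only follow-up period written for these subjects is 30 days, while the primary analysis needs their status at day 180. This should be fixed, because a site following the specific sentence could lose primary-endpoint data that are obtainable.

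Whether any bias results is not established. It requires that contact actually stops at day 30 and that prognosis after day 30 differs by implant status. Across the scenarios examined, the shift in AFS runs from −0.47 to +0.92 points. At a failed-implant AFS of 42.3%, only the 10% failure rate puts type I error clearly above 0.025 in both simulations. No stated sample size, threshold or power figure is wrong on this account.

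**What to change.** Revise protocol section 5.5 and Table 1 footnote 10 to say that AFS status (alive or dead, major amputation of the index limb or not) is ascertained through day 180, by phone or record check, for every mITT subject, including failed and non-attempted implants. Reconcile the 30-day wording with the synopsis follow-up period, footnote 9, section 8.5, section 11.5.2 and SAP 6.4.

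SAP section 4 shows that the N=90 assessment had already taken place when the maximum was revised. The change must therefore also cover subjects already enrolled, with status recovered retrospectively where contact has ended.

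Leave the primary analysis as it is. No new sensitivity analysis is needed: report how many failed implants lack day-180 status, and point out within the planned tipping-point analysis the combination that counts them as events.

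The cost is two protocol sentences, a few calls or record checks per affected subject, and one reported count. The primary test and its operating characteristics do not change. The estimated AFS may fall slightly.

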### 5.6 Intra-operative

For consented subjects that meet the pre-operative eligibility criteria, the following data regarding their endovascular procedure will be recorded:

- Target In-Flow Artery (cross-over point), including proximal reference vessel diameter (RVD) and assessment of calcification or any other abnormalities
- Target Out-Flow Vein (cross-over point) characteristics
- Intra-operative anticoagulants administered, and corresponding ACT levels
- Pre- and post-procedural angiographic images showing flow to the foot
- Procedure start and finish times
- Total contrast amount given
- Total fluoroscopic milligray for the procedure

- Documentation of any device- or procedure-related adverse events
- Technical Success

At the end of the endovascular procedure, with the procedural sheath in place and under fluoroscopic visualization, an injection of contrast may be made to assess the anatomy, placement, and patency of the proximal, body and distal ends of the LimFlow stent graft.

### 5.7 Post-Operative

After the LimFlow System is successfully placed, the access site and peripheral extremity should be closely monitored. All subjects will undergo a continuous wave Doppler exam distal to the stent graft immediately following the completion of the procedure and again between 4 and 30 hours post-procedure. The exam is intended to verify the patency of the LimFlow stent graft and assess for acute stent graft thrombosis. Any findings of acute stent graft thrombosis must be reported as an adverse event within 24 hours.

### 5.8 Follow-up

Study subjects will be asked to undergo evaluation prior to and during the course of the clinical trial. Such tests and procedures are outlined in the Study Assessment Schedule.

Subjects should return to the clinic at 14 days (+/- 3 days), 1 month (+/- 1 week), at 2, 3, 6, and 9 months (+/- 2 weeks), and then annually (+/- 4 weeks) for up to 3 years following their endovascular procedure and the peripheral limb/wound should be assessed. For the purposes of this study, 1 “month” will equal 30 calendar days, e.g., 3 months would be equivalent to 90 days. For the purposes of this study, 1 “year” will equal 365 calendar days, e.g., 2 years would be equivalent to 730 days.

Visits or tests occurring outside of the specified date range will be considered protocol deviations. All protocol deviations, including visits outside of the protocol allowable window, will be documented and reported. Subject compliance with follow-up is critical. Lack of or incomplete follow-up may present a risk to the subject and may compromise study results. For subjects out of area or who refuse to come in for a follow-up visit, a telephone assessment should be conducted to capture as much information as possible at this time point.

Routine surveillance of the wound and index limb will be performed during each follow-up visit, in accordance with ACC/AHA 2006 Peripheral Disease Guidelines. Examinations will include assessments of pulse, pain, Rutherford Classification, WIfI Classification, wound healing status, medication regimen (antiplatelets, anticoagulants, antibiotics, and other pertinent medications that may affect wound healing) and any procedures or complications related to the index limb occurring since the last visit. In the event of a major amputation of the target limb, the LimFlow Stent Grafts may be harvested for evaluation.

The limb/wound will be photographed by trained personnel using the eKare Insight® system. Refer to the eKare Insight Training for photograph protocol. The eKare inSight digital wound management platform (eKare, Inc., Fairfax, Virginia, United States of America) will be used for photographing, scanning, and assessing wounds at screening and follow-up visits. eKare inSight will be provided to sites for use during the study by the Sponsor. eKare is ISO 13485 certified and is fully compliant with FDA 21 CFR Part 820, Part 11.

### 5.9 Study Exit or Premature Withdrawal

Subjects will be exited from the study by completion of a Study Exit eCRF. Subjects will be exited upon completion of the follow-up visits, withdrawal of consent, or instance of meeting a primary study endpoint (major amputation or death). Following study exit, the subject will undergo the standard medical care for their condition as determined necessary and appropriate by their physician.

Subjects may be prematurely exited or withdrawn from the study for, including but not limited to, the following reasons:

- Voluntary withdrawal – meaning that the subject voluntarily chooses not to further participate in the study
- Lost to follow-up – meaning that the subject is more than 14 days out of window of a study visit and 3 documented attempts to contact the subject are unsuccessful. A subject who misses two consecutive study visits, including phone contact, will be considered lost to follow-up. A missed visit will be considered a protocol deviation and the deviation will be documented and reported.
- In the physician’s opinion, it is not in the best interest of the subject to continue study participation.

All subjects enrolled (including those withdrawn or lost to follow-up) shall be accounted for and documented.

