**Follow-Up Schedule**

Measures of safety and effectiveness will be assessed through hospital discharge, at 14 ( $\pm$  3) days, 30 ( $\pm$  7) days, at 2, 3, 6, and 9 months ( $\pm$  2 weeks), at one year ( $\pm$  4 weeks), two years ( $\pm$  4 weeks), and three years ( $\pm$  4 weeks). The study will be completed and closed after all subjects have either met a primary endpoint or completed the 3-year follow-up requirements.

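### Subjects leave the study at major amputation, and nothing provides for collecting their new SAEs or vital status afterwards, although the protocol asks for all SAEs to 6 months

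*Protocol*

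**What the plan says.** **Exit rule.** Protocol Section 5.9 lists completion of visits, withdrawal of consent, or "instance of meeting a primary study endpoint (major amputation or death" as triggers for exit. It continues: "Following study exit, the subject will undergo the standard medical care for their condition". The Follow-Up Schedule in the protocol synopsis agrees, since the study closes "after all subjects have either met a primary endpoint or completed the 3-year follow-up requirements". SAP Section 1 repeats that closure sentence.

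**Data requirements.**
- Protocol Section 8.5: "all serious adverse events (SAE) will be reported and monitored from the time of treatment through the 6-month follow-up visit".
- Protocol Table 1, footnote 9: "all SAEs through 6 months".
- Protocol Section 8.5, on the index limb: "Any SAEs related to the index limb will be reported and monitored throughout the 3-year follow-up visit".
- Protocol Table 1: the row "All-cause mortality" is ticked at every visit from treatment (Visit 2) to 3 years (Visit 11).

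None of these makes an exception for a subject who has had a major amputation.

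**Analysis.** SAP Section 8 tabulates adverse events as numbers and percentages of enrolled subjects up to milestone times. It has no person-time denominator and no adjustment for early exit.

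**The concern.** A site that follows Section 5.9 closes the record of an amputee on the day of the amputation. A site that follows Section 8.5 keeps reporting SAEs to 6 months. Both can claim to comply, so ascertainment may differ between sites.

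Under the exit rule, an amputee stays in the SAP Section 8 denominator but has no route by which a new event can enter the numerator. SAE percentages, and any crude count of deaths, can then err only downwards. The loss is informative because it falls on subjects in whom the procedure failed. The trial's objective is safety as well as effectiveness, and the DMC's recommendations on continuing the study rest on the same safety record (Protocol Section 7.3).

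**Working it through.** **1. The passages side by side**

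| Item | Required by | Available for an amputee after exit |
|---|---|---|
| New SAEs to 6 months | Section 8.5; Table 1 footnote 9 | No route stated |
| New index-limb SAEs to 3 years | Section 8.5 | No route stated |
| Vital status to 3 years | Table 1 mortality row | No route stated |
| SAEs already reported at exit | Section 8.1 | Followed until resolved, stable or explained |

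The first two rows are the direct conflict. The third is a scheduled item that would stay empty for amputees. The fourth is a partial safeguard.

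**2. Which endpoints are touched.** Amputation already counts as a failure for AFS, for limb salvage and, within 30 days, for procedural success. Later follow-up cannot change these. The affected outputs are the SAP Section 8 tables and any count of deaths.

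**3. The SAP's planning event curve, reproduced.** Inputs are the four hazards per day in SAP Section 6.7: 0.005417298, 0.00647187, 0.004045362 and 0.0015350038, over intervals of 30, 30, 30 and 90 days. The formula is S(t) = exp(−Σ hazard × days).
- The interval contributions are 0.1625, 0.1942, 0.1214 and 0.1382, which sum to 0.6162.
- S(30), S(60), S(90) and S(180) are 0.85, 0.70, 0.62 and 0.54, as the SAP states.

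**4. Scaling to AFS 0.70.** The SAP multiplies all hazards by a constant: k = ln(0.70)/ln(0.54) = 0.579. This gives S(30) = 0.910, S(60) = 0.813, S(90) = 0.758 and S(180) = 0.700.

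**5. Mean event time among subjects with an event by day 180.** The formula is [∫S(t)dt from 0 to 180 − 180 × S(180)] / [1 − S(180)]. Each interval contributes (S at start − S at end) / scaled hazard to the integral.
- Integral: 28.6 + 25.8 + 23.6 + 65.6 = 143.6 days.
- Mean event time: (143.6 − 126.0) / 0.30 ≈ 58.7 days.
- Remainder of the window: 180 − 58.7 = 121.3 days.

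At AFS 0.54 the same steps give a mean of 55.6 days and a remainder of 124.4 days.

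**6. Number of subjects at N = 105 (the SAP maximum).** The documents do not say what share of first events are amputations; one third to two thirds is assumed.

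| True AFS | Six-month events | Exits at amputation | Share of enrolled | Share of all 6-month follow-up time lost |
|---|---|---|---|---|
| 0.70 | 105 × 0.30 = 31.5 | 10.5 to 21.0 | 10% to 20% | 6.7% to 13.5% |
| 0.54 | 105 × 0.46 = 48.3 | 16.1 to 32.2 | 15% to 31% | 10.6% to 21.2% |

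The last column is exits × remaining days / (105 × 180), for example 10.5 × 121.3 / 18,900 = 6.7%. It assumes that amputations have the same timing as the composite event.

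**The case against.** **The documents can be read as consistent.** The exit rule appears in three places and looks deliberate, and follow-up is described as up to 3 years, which allows early exit. Table 1 also ticks Rutherford class, wound healing and stent-graft duplex at late visits with no exception for amputees, so it may list assessments only for subjects still on study. This stands for the mortality row, which alone does not promise follow-up after exit. It is weaker against Section 8.5 and footnote 9, which fix the SAE window by time from treatment and ask for all SAEs. Even those could be read as applying only while a subject is on study, which is why the text needs settling.

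**Some later deaths could still be captured.** A reader might infer that deaths and SAEs after amputation are never recorded. The documents do not support that. Section 8.1 follows reported SAEs until resolved or explained, and Section 8.4 records amputation as a treatment and death as an outcome of an adverse event. A death arising from an SAE still open at amputation could therefore be recorded. The gap is in new events and in vital status generally.

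**Little of the planned analysis depends on this.** Overall survival is not among the endpoints in Protocol Section 4.8 or SAP Section 3.2, and no mortality-rate analysis is specified. This stands. The effect is on safety tabulation, not on a planned survival estimate.

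**The change has a real cost in a running trial.** SAP Section 4 shows that the N = 90 assessment had already taken place, so some subjects may already have exited. The telephone option in Section 5.8 covers subjects who are out of area or decline a visit, not those already exited. This also stands.

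**Conclusion.** The concern holds in a limited form. The exit rule conflicts with the SAE windows in Section 8.5 and footnote 9, leaves the mortality row unfilled for amputees, and is not offset by any provision for new events or vital status after exit. SAE percentages over enrolled subjects and any count of deaths can only be understated, selectively in treatment failures.

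For scale, about 10 to 21 of 105 subjects would be affected at AFS 0.70, each losing about two thirds (121/180) of the 6-month SAE window. Two assumptions carry these figures: the amputation share of first events, and amputation timing that matches the SAP planning curve. The conflict in the text depends on neither.

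Two stronger inferences should not be drawn. The primary result is not biased, because amputation is itself an AFS event; alpha, power and sample size are unchanged. Nor can a number of missed deaths be given, since the documents contain neither the amputation share nor mortality after amputation over either window.

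**What to change.** Reconcile Section 5.9 and the closure sentence (protocol and SAP synopses) with Section 8.5 and Table 1:

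- Major amputation ends limb, wound and graft assessments only. Exit occurs at death, withdrawal, loss to follow-up or completion of 3 years.
- SAE contact continues to 6 months and vital status to 3 years, by telephone at the existing visit times. Telephone follow-up is already used in Section 5.8, in Table 1 footnote 9, and in Section 5.5 for subjects without an implant.
- State explicitly how the 3-year requirement for index-limb SAEs applies after amputation.
- In SAP Section 8, report SAEs and deaths in all mITT subjects, with the number whose follow-up was truncated at amputation.
- For subjects already exited, seek vital status where consent and IRB/EC approval allow.

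The cost is a protocol amendment with IRB/EC approval, a modest site workload of a few calls per amputee, and possible re-contact and re-consent of subjects already exited.
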